2 ANALYSIS POPULATIONS

The following populations for analyses are defined.

Table 3 - Populations for analyses

Population	Description
Screened	All participants who signed the ICF.
Intent-to-treat (ITT)	All randomized participants. Participants will be analyzed according to the intervention allocated by randomization.
Per-protocol (PP)	All participants from ITT population who have completed 24 weeks of randomized treatment and did not start any rescue therapy before end of the 24-week randomized treatment period and have no major or critical protocol deviation that can potentially affect efficacy analysis. The protocol deviations for PP exclusion are defined in Section 5.7 and will be confirmed and finalized for each patient prior to the database lock. Participants will be analyzed according to the intervention allocated by randomization.
Safety	All randomized participants who have taken at least 1 dose of study intervention, regardless of the amount of treatment administered. Participants will be analyzed according to the intervention they actually received.

Participants exposed to study intervention before or without being randomized will not be considered randomized and will not be included in any analysis population. The safety experience of these participants will be reported separately.

Randomized participants for whom it is unclear whether they took the study intervention will be considered as exposed and will be included in the safety/population as randomized.

For any participant randomized more than once, only the data associated with the first randomization (except if the first randomization is done by error) will be used in any analysis population. The safety experience associated with any later randomization will be reported separately.

For participants receiving more than one study intervention during the study, the intervention group for as-treated analyses will be the intervention group as randomized if the participant received at least one administration as randomized.

3 STATISTICAL ANALYSES

3.1 GENERAL CONSIDERATIONS

In general, continuous data will be summarized using the number of observations available, mean, standard deviation (SD), median, minimum, and maximum. Categorical and ordinal data will be summarized using the count and percentage of participants.

The baseline value is defined as the last available value before the first injection of open label investigational medicinal product (IMP). For participants randomized but not treated, the baseline value is defined as the last available value before randomization.

Unless otherwise specified, analyses will be performed by intervention group (and overall for baseline and demographics characteristics).

Observation period

The observation period will be divided into 3 segments:

- The **pre-treatment period** is defined as the period up to first injection of open-label IMP.
- The **on-treatment period** (ie, treatment-emergent (TE) period) is defined as the period from the first injection of open-label IMP to the last injection of IMP + 3 days (1 day for hypoglycemia).
- The **post-treatment period** is defined as the period from the end of the on-treatment period.

3.2 PRIMARY ENDPOINT(S) ANALYSIS

3.2.1 Definition of endpoint(s)

The primary endpoint is the absolute change from baseline to week 24 in HbA1c. All the efficacy assessments collected during the study will be used, including those obtained after treatment discontinuation or initiation of rescue therapy (refer to [Section 5.5](#) for definition).

3.2.2 Main analytical approach

The null and the alternative hypotheses based on non-inferiority margin of 0.3% are described as:

$$H_0: i\text{GlarLixi} - \text{IDegAsp} \geq 0.3\% \text{ versus } H_a: i\text{GlarLixi} - \text{IDegAsp} < 0.3\%$$

If the upper bound of the two-sided 95% confidence interval for the difference of iGlarLixi – IDegAsp is smaller than 0.3%, the study will be considered to have met its primary objective and the non-inferiority of iGlarLixi over IDegAsp is established.

The primary endpoint will be analyzed with the primary estimand defined according to the following attributes:

- Endpoint: Change in HbA1c from baseline to Week 24.
- Treatment condition: iGlarLixi will be compared to IDegAsp.
- Analysis population: All randomized participants
- Intercurrent events (IE):
 - Treatment discontinuation IE will be handled with the treatment policy strategy: the endpoint will be assessed based on all assessments irrespective of the treatment discontinuation
 - The initiation of rescue medication IE will be handled with the treatment policy strategy: the endpoint will be assessed based on all assessments irrespective of the initiation of rescue medication
- Population-level summary: LS Means difference between treatments from analysis of covariance (ANCOVA) with treatment groups and previous OADs as fixed effects, and baseline HbA1c continuous value as covariate. Standard errors (SE), 2-sided 95% confidence intervals (CI) and 2-sided non-inferiority p-value from ANCOVA will be provided. Missing data will be imputed by multiple imputations using missingness patterns based on treatment completion, and under the missing at random (MAR) assumption within each pattern.
 - For participants completing the 24-week treatment period, the missing HbA1c values will be imputed using data from other participants completing the treatment.
 - For participants discontinuing prematurely the treatment, the missing HbA1c values will be imputed using data from participants also discontinuing treatment but having their HbA1c assessment (retrieved dropouts). In case there are not enough observed Week 24 data post treatment discontinuation, ie, less than 10 in either arm, or the model does not converge, whichever happens, return-to-baseline (RTB) approach will be used for imputation; missing HbA1c values at Week 24 will be imputed from a normal distribution with the expected value set to the participant's baseline value and standard deviation based on the baseline value by treatment group.

Missing HbA1c values will be imputed 1000 times to generate 1000 datasets with complete HbA1c values using SAS procedure for multiple imputation (PROC MI). The imputation model will include the treatment group as fixed effect, and baseline, Week 8, Week 12 and Week 18 HbA1c continuous value as covariate. The randomization stratum of HbA1c can be removed from the model given that the baseline HbA1c continuous value is already in the model.

For each of the 1000 imputed datasets, the change in HbA1c from baseline to Week 24 will be analyzed using an ANCOVA with treatment groups and previous OADs as fixed effects, and baseline HbA1c continuous value as covariate. The results obtained from analyzing the datasets will be combined using Rubin's rule to draw inference.

The non-inferiority will be assessed using the upper bound of the 2-sided 95% confidence interval (CI). If the upper bound of the 95% CI is less than 0.3%, the non-inferiority of iGlarLixi versus IDegAsp will be claimed.

Descriptive statistics for HbA1c results and changes from baseline will be provided for baseline and each visit by treatment group. Mean changes from baseline with the corresponding standard error will be plotted over time.

Missing data assumption check

The following analyses will be performed on the ITT population to explore the missing data frequency and pattern in the primary efficacy analysis:

- To explore missing data patterns for HbA1c in the primary efficacy analysis, number (%) of participants and number (%) of participants by baseline characteristics will be presented by the following missing data pattern and by treatment group. Descriptive statistics and plots for HbA1c results and changes from baseline will be provided by missing data pattern and by treatment group:
 - Pattern 1: participants who have completed treatment and have Week 24 HbA1c value,
 - Pattern 2: participants who have completed treatment and do not have Week 24 HbA1c value,
 - Pattern 3: participants who have not completed treatment and have Week 24 HbA1c value,
 - Pattern 4: participants who have not completed treatment and do not have Week 24 HbA1c value.
- Baseline characteristics and HbA1c values by visit will be presented by missing data pattern for each treatment group, using descriptive statistics and/or graphs.
- Further exploratory analyses will be performed to evaluate factors influencing missing data: for each baseline characteristic, a logistic regression will be performed to model the missingness (Yes, No) at Week 24. The model will include fixed-effect terms for treatment group, the categorical fixed-effect term or continuous fixed covariate of the studied baseline characteristic and the interaction between treatment group and covariate studied. Estimates and p-value will be provided for descriptive purpose. A separate model will be run for each baseline characteristic. Additional multivariate analyses may be performed if needed.

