| HbA1C | X | | | | | X | | X | | X | | X | | X | X | |

| Study period | Screening | Randomization | Study treatment period | | | | | | | | | | | | | Follow-up |
|---|-----------|----------------|------------------------|------|---|------|---|------|----|------|----|------|----|----------------|------------------|-------------|
| Visit number | 1 | 2 ^a | 3 | 4 | 5 | 6 | 7 | 8 | 9 | 10 | 11 | 12 | 13 | 14 | E/D ^d | 15 |
| Visit type (on-site/phone) ^b | site | site | ☎ | site | ☎ | site | ☎ | site | ☎ | site | ☎ | site | ☎ | site | site | ☎ |
| Week ^b | -2 | 0 (Day 1) | 1 | 2 | 3 | 4 | 6 | 8 | 10 | 12 | 15 | 18 | 21 | 24 | E/D | 24 + 3 days |
| FPG ^m | X | X | | | | X | | X | | X | | X | | X | X | |
| Fasting C-peptide ^m | | X | | | | | | | | | | | | X ⁿ | X | |
| Safety laboratory ^k hematology, serum chemistry | X | | | | | X | | X | | X | | X | | X | X | |
| Amylase, lipase, calcitonin | X | | | | | X | | X | | X | | X | | X | X | |
| FSH, estradiol (if necessary to confirm menopausal status) | X | | | | | | | | | | | | | | | |
| Urine pregnancy test ^l (women childbearing potential only) | X | X | | X | | X | | X | | X | | X | | | | |

- a Randomization (V2) can be performed less than 2 weeks after screening visit (V1) if the laboratory data are available.
- b Additional phone calls between visits for titration purposes should be scheduled as often as deemed necessary by the Investigator
- c Visit widows listed in the table are acceptable always using Day 1 (V2) as reference. A visit window of -1 day or +3 days for the post-treatment follow-up visit (V15) is acceptable using the day of V14 as reference. If one visit date is changed, the next visit should take place according to the original schedule.
- d **E/D= Early IMP discontinuation**, participants should have an onsite visit as soon as possible with the assessments (except 7-point SMPG) normally planned at the end of treatment visit (V14). Afterward, the patients should continue in the study up to the scheduled date of study completion. They should be followed up according to the study procedures as specified in the protocol. **In case of rescue therapy**, all assessments (except 7-point SMPG) planned at V14 should be performed before starting rescue therapy, participants then continue the study treatment (including background therapy if appropriate), and all visits and assessments should be performed as scheduled.
- e Systolic and diastolic blood pressure, heart rate.

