Missing HbA1c values will be imputed 1000 times to generate 1000 datasets with complete HbA1c values using SAS procedure for multiple imputation (PROC MI). The imputation model will include the treatment group, as fixed effect, and baseline HbA1c continuous value as covariate. The randomization strata of HbA1c can be removed from the model given that the baseline HbA1c continuous value is already in the model.

For each of the 1000 imputed datasets, the change in HbA1c from baseline to Week 24 will be analyzed using an ANCOVA with treatment groups and previous OADs as fixed effects, and baseline HbA1c continuous value as covariate. The results obtained from analyzing the datasets will be combined using Rubin's rule to draw inference. The non-inferiority will be assessed using the upper bound of the 2-sided 95% confidence interval (CI). If the upper bound of the 95% CI is less than 0.3%, the non-inferiority of iGlarLixi versus IDegAsp will be claimed.

Sensitivity analyses of primary estimand

The following sensitivity analyses will be performed for the primary estimand.

- The primary endpoint will be analyzed using a mixed-effect model with repeated measures (MMRM), under the missing at random framework. The model will include treatment, previous OADs, visit, treatment-by-visit interaction as fixed effects, and baseline HbA1c value as continuous covariate. The randomization strata of HbA1c can be removed from the MMRM model given that the baseline HbA1c value is already in the model. The MMRM model will be implemented using SAS® (Version 9.4 or higher) MIXED procedure (PROC MIXED) with an unstructured correlation matrix to model the within-participant errors. Parameters will be estimated using the restricted maximum likelihood method with the Newton-Raphson algorithm. Denominator degree of freedom will be estimated using the Kenward-Roger approximation by fitting values from post-randomization scheduled visits.

Primary analysis for the secondary estimands

Under hypothetical strategy, measurements after treatment discontinuation and/or initiation of rescue medication will be considered as missing data.

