1.1 STUDY DESIGN

- Open-label, 1:1 randomized, active-controlled, 2 treatment-arm, 24-week treatment duration, parallel-group, multicenter phase 3 study
- Participants with type 2 diabetes mellitus (T2DM) treated with metformin ± one additional oral antidiabetic drug (OAD) would be recruited in this study.
- The randomization will be stratified by value of screening HbA1c (<8%, ≥8%), and by use at screening of metformin alone or metformin + SGLT-2i (Yes/No), ie, by oral antidiabetic treatment use at screening (metformin ± SGLT-2i / metformin + OAD other than SGLT-2i). The overall objective of this last stratification group is to ensure that participants who will need to discontinue their second OAD are well balanced between groups
- Total duration of study participation for each participant is up to 27 weeks.
- This study comprises of 3 periods:
 - An up-to 2-week screening period during which: a sulfonylurea (SU), a glinide, an alpha-glucosidase inhibitor (alpha-GI), or a dipeptidyl-peptidase-4 (DPP-4) inhibitor, if previously taken, will be discontinued. Sodium-glucose co-transporter 2 (SGLT-2) inhibitor, if previously taken, will be kept at the stable dose; metformin treatment will maintain at the stable dose (at least 1000 mg/day or a maximal tolerated dose).
 - A 24-week, open-label randomized treatment period with iGlarLixi or IDegAsp, both on top of metformin ± SGLT-2 inhibitor.
 - A 3-day post-treatment safety follow-up period.
- Screening is from signed informed consent to randomization.

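### The primary imputation model omits previous OADs, a randomization stratum that the analyses of the imputed HbA1c data adjust for; the likely bias is small and the repair is cheap

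*SAP*

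**What the plan says.** Randomization is stratified by screening HbA1c and, in the words of SAP 1.1, "by oral antidiabetic treatment use at screening (metformin ± SGLT-2i / metformin + OAD other than SGLT-2i").

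SAP 3.2.2 imputes missing HbA1c within two patterns: treatment completers from other completers, and discontinuers from retrieved dropouts. On the predictors it says: "The imputation model will include the treatment group as fixed effect, and baseline, Week 8, Week 12 and Week 18 HbA1c continuous value". One stratum is then accounted for: "The randomization stratum of HbA1c can be removed from the model given that the baseline HbA1c continuous value is already in the model". Nothing is said about the other. Each completed dataset is analysed "using an ANCOVA with treatment groups and previous OADs as fixed effects", with baseline HbA1c as covariate.

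Protocol 9.3.2 has the same gap and uses no post-baseline visits: "The imputation model will include the treatment group, as fixed effect, and baseline HbA1c continuous value as covariate". The SAP therefore lengthened the predictor list but did not add the stratum.

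Elsewhere the stratum is used. The MMRMs in SAP 3.2.3 and 3.2.4 include previous OADs. SAP 3.7.2 reuses the primary imputed datasets for a subgroup analysis by OAD stratum. SAP 3.3.1.2 carries the same imputation method to body weight (endpoint 2b), whose ANCOVA also adjusts for previous OAD.

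**The concern.** An imputation model should normally contain every variable in the analysis model. Otherwise the imputed values are drawn as if the omitted variable had no further relation to the outcome, and the analysis then estimates that relation from data in which it has been diluted. Missing at random also becomes less plausible, because it has to hold without conditioning on the stratum.

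There is reason to expect this stratum to matter. One group stops its second OAD around randomization and the other keeps its regimen (Protocol 4.1 and 6.8.1). Protocol 4.1 says that balancing the participants who must stop a drug is the purpose of the stratification.

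At stake is a small bias in the primary treatment difference. There are also two matters of coherence. The primary analysis and its MMRM sensitivity analysis condition on different variables, which blurs any comparison between them. The OAD subgroup analysis uses values generated without the factor that defines the subgroups.

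**Working it through.** **1. The plan's sample size.** Inputs from SAP 4: margin 0.3%, SD 1.05%, true difference 0, two-sided 0.05, power 90%, dropout 10%.

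n per arm = 2 × (1.960 + 1.282)² × 1.05² / 0.3² = 257.4, so 258 (259 with the noncentral t). Dividing by 0.90 gives 287 to 288 per arm, or 574 to 576 in total, against the stated 580. With 290 × 0.90 = 261 evaluable per arm, power is 0.903. The figure is reproduced, and the point below does not change it.

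**2. Model terms side by side.**

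| Model | Previous OADs | HbA1c terms |
|---|---|---|
| Imputation, Protocol 9.3.2 | no | baseline |
| Imputation, SAP 3.2.2 | no | baseline, Weeks 8, 12, 18 |
| ANCOVA on imputed data, SAP 3.2.2 | yes | baseline |
| MMRMs, SAP 3.2.3 and 3.2.4 | yes | baseline by visit |
| OAD subgroup on the same imputed data, SAP 3.7.2 | yes, with treatment interaction | baseline |

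**3. When bias arises.** To first order, if missing participants have no usable post-baseline value,

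bias ≈ b × m × (g_T − g_C),

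where b is the stratum effect on Week 24 HbA1c, m the missing fraction, and g the share of the higher-HbA1c stratum among the missing minus its share among the observed, in each arm. If the gap is the same in both arms, the bias is zero.

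The documents give neither b nor the missingness by stratum. All values below, apart from 290 per arm, the SD of 1.05% and the 10% average dropout, are assumptions. Strata are taken as equal in size.

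- Moderate: b = 0.3%, missingness 15% and 5% by stratum, reversed in the other arm. Share among missing 0.15/0.20 = 0.750; among observed 0.85/1.80 = 0.472; gap 0.278, and −0.278 in the other arm. Bias ≈ 0.3 × 0.10 × 0.556 = 0.017%.
- Extreme: b = 0.6%, missingness 18% and 2%, reversed. 0.18/0.20 = 0.900; 0.82/1.80 = 0.456; gap 0.444. Bias ≈ 0.6 × 0.10 × 0.889 = 0.053%.

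These are ceilings. Week 8, 12 and 18 values are in the model and carry part of the stratum effect for anyone who has them.

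**4. Simulation.** 580 participants, 400 trials, 15 imputations, true difference zero, dropout starting at any visit from Week 8 to Week 24, analysed by the planned ANCOVA with Rubin's rules. Entries are the mean estimated treatment difference (%).

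| Scenario | SAP model | Stratum added | Shift | Mean SE, SAP / added |
|---|---|---|---|---|
| b = 0.3, missingness unrelated to stratum | −0.0083 | −0.0077 | 0.0006 | 0.0898 / 0.0898 |
| b = 0.3, 15%/5% reversed | −0.0034 | 0.0031 | 0.0065 | 0.0899 / 0.0898 |
| b = 0.6, 18%/2% reversed | −0.0216 | 0.0002 | 0.0218 | 0.0904 / 0.0901 |

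The Monte Carlo error of each mean is about 0.086/√400 = 0.004, so the shift between models on the same simulated trials is the quantity to read. It is about 40% of the ceiling (0.0065/0.0167 and 0.0218/0.0533), as expected when later visits carry the rest.

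A second simulation (b = 0.4%, half of dropouts with no HbA1c after Week 4, 5% against 20% missing by stratum in one arm) gave −0.0128 without the stratum and −0.0011 with it. With balanced missingness it gave −0.0037 and −0.0038. The order of magnitude agrees.

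**The case against.** The strongest reply is that nothing here would change a conclusion. The largest simulated shift is 0.0218/0.3 = 7% of the margin and about a quarter of a standard error near 0.09, and it needs an extreme pattern. That stands, and it sets the grade of the point.

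A second reply is that the plan already covers the risk. SAP 3.2.2 regresses Week 24 missingness on each baseline characteristic with a treatment interaction, and SAP 5.3 lists the OAD stratum among those characteristics. The MMRM in SAP 3.2.3 includes previous OADs, although its listed visits stop at Week 18, which is a separate matter. The penalised imputation adds 0.3% to imputed iGlarLixi values, which at 10% missing moves that arm's mean by 0.10 × 0.3 = 0.03%, more than any simulated shift. This stands in part. These analyses would reveal or bracket the problem, but none corrects the primary estimate.

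Third, baseline HbA1c already absorbs the different entry ranges of the two strata (Protocol 5.1), and later visits absorb much of the effect of stopping a drug. This is fair, and it is why the simulated shift falls below the ceiling. It does not help participants with no value from Week 8 on.

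Fourth, saying that the HbA1c stratum can be removed may imply that the OAD stratum stays. That is possible, but the sentence listing the terms does not name it, so the text needs settling either way.

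Fifth, the retrieved-dropout model is small. The fallback applies when there are too few, "ie, less than 10 in either arm, or the model does not converge, whichever happens, return-to-baseline (RTB) approach will be used". With 10 per arm, about 20 participants already support six mean parameters (intercept, treatment and four HbA1c values). This stands and limits the fix. Where the fallback is triggered, the listed model applies only to completers without a Week 24 value.

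**Conclusion.** The mismatch is real: the primary imputation omits a randomization stratum that the analysis of the imputed data includes, and the SAP gives no reason. Its effect is small: a shift of about 0.001% to 0.022% for stratum effects of 0.3% to 0.6% and 10% average missingness, and negligible when missingness is balanced. The direction depends on which arm loses more of the higher-HbA1c stratum. These sizes rest on assumed stratum effects, visit correlations and dropout patterns. The tabulated simulation imputed all missing participants with one model, not by treatment-completion pattern, and did not apply the return-to-baseline fallback.

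A reader might infer that the non-inferiority conclusion is in doubt. The documents do not support that. No figure in them implies missingness by stratum that differs between arms. Even in the extreme scenario, the share of simulated trials meeting the margin was 0.963 with the SAP model and 0.938 with the stratum added.

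A reader might also infer that Week 4 HbA1c, which is sampled and windowed, should join the model. That does not follow. Adding it lowered the mean SE by under 1% (0.0898 to 0.0892 with balanced missingness) and did not reduce bias in the second simulation (−0.0011 before, −0.0017 after). HbA1c reflects about 120 days (Protocol 3.1), so a Week 4 value is largely pre-treatment. The HbA1c MMRMs that name their visits also begin at Week 8, which looks like a consistent choice.

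**What to change.** In SAP 3.2.2, add the previous-OAD randomization stratum as a fixed effect in the imputation model for treatment completers. Add it to the retrieved-dropout model where the number of retrieved dropouts supports it, and state that condition before database lock. If the stratum is left out of either model on purpose, give the reason, as is done for the HbA1c stratum. Body weight (2b) and the other continuous endpoints that reuse the method should follow the same rule.

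For completers the cost is close to nil: the stratum is recorded for everyone at randomization, and the sample size and the ANCOVA are unchanged. In the retrieved-dropout model it is one more parameter, seven in place of six, on possibly 20 participants, with a binary factor that may be sparse. Non-convergence there would switch discontinuers to return-to-baseline, so the term should not be forced in.
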